Is the topographic classification of placenta accreta spectrum useful in determining possible clinical outcomes? How acceptable it is by obstetrician-gynecologists who manage PAS?

RESEARCH HYPOTHESES

The topographic classification of placenta accreta spectrum is useful in determining possible clinical outcomes. The topographic classification has high acceptability among obstetrician-gynecologists who manage PAS.

OBJECTIVES

- *General*

To evaluate the clinical outcomes of patients with a diagnosis of placenta accreta spectrum according to the topographic classification, and to explore the acceptability of this classification among obstetrician-gynecologists at the participating medical centers.

- *Specific*

1. To describe the demographic and clinical characteristics of patients with a diagnosis of placenta accreta spectrum.
2. To analyze the clinical outcomes of patients diagnosed with placenta accreta spectrum according to the topographic classification.
3. To explore the acceptability of the topographic classification for placenta accreta spectrum among obstetrician-gynecologists at the participating medical centers.

EXPECTED RESULTS

The aim of this study is to describe the demographic and clinical characteristics of patients with a diagnosis of placenta accreta spectrum, and to determine the correlation between the topographic classification and the clinical outcomes found in the study. Finally, to evaluate whether the proposed classification is accepted by the obstetrician-gynecologists of the participating centers that manage placenta accreta spectrum patients.

METHODOLOGY

Design:

1. Multicentric study of a prospective cohort.

It is clarified that this is an observational study, in which data will be obtained from the medical records and other documents in each participating center, which are considered to be of routine use in day-to-day clinical practice. The study of the outcomes proposed in this protocol will be limited to those recorded in the clinical records and will be taken into account until the participant is discharged

from the hospital, during which a surgical intervention was performed due to the suspicion or diagnosis of PAS.

Study population:

1. Pregnant patients with a diagnosis of placenta accreta spectrum who visits any of the participating medical centers.
2. Obstetrician-gynecologists working in participating medical centers.

Participating centers:

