Once the collection of patient data has been completed, the survey to evaluate the acceptability of the topographic classification of PAS will be administered to the group of obstetricians who manage placenta accreta at the participating centers. Each participating physician who has applied the topographic classification to the patients treated during the study period, will complete the survey only once at the end of the study period.

This information will be typed and stored in the RedCap platform. At Fundación Valle del Lili, the task will be performed by the research assistants' that are part of the principal investigators team, and in the participating hospitals by delegates designated by each center. The extraction and collection of data will be supervised by the principal investigator, with prior authorization from the ethics committee.

For the quality analysis, 10% of the data will be randomly sampled and compared with the medical records or paper-based documents. If there is discordance between the data, another 10% will be randomly analyzed and if there is still discordance, the entire database will be revised. This task will be the responsibility of each participating center, in relation to the number of patients admitted by them.

Data Management and Statistical Analysis

Specific Objective 1: To describe the sociodemographic and clinical characteristics of patients with a diagnosis of placenta accreta spectrum.

Descriptive Analysis: Stratification by subgroups will be performed according to the topographic classification of PAS, as follows: T1, T2a, T2b, T3, T4, T5a and T5b. Qualitative variables will be summarized as percentages and presented as absolute frequencies. For quantitative variables, the normality distribution will be determined by means of the Kolmogorov Smirnov statistic (sample size greater than 50 patients is foreseen), where a result of p value >0.05 would comply with the assumption of normality. For variables with normal distribution, mean and standard deviation will be determined; and for variables without normal distribution, median and interquartile ranges (Q1 - Q3) will be indicated.

Inferential Analysis: For quantitative variables, a statistical test of the difference between the means of the 7 subgroups (independent groups) will be performed by means of one-way ANOVA for independent groups. If the variable does not have a normal distribution, the Kruskal-Wallis test will be performed.

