- b) The following item is added: *The application of the anatomical classification for PAS generates an additional consumption of resources*. It is considered important to ask about that consideration, taking into account that the proposed classification will be very useful in low- and middle-income countries with limited healthcare systems.
- c) Item withdrawn: *The evidence supporting the norm is flawed*, as there are not enough studies addressing the present classification; therefore, it is not relevant to include the item.
- d) The following item is removed: *I am already following another norm or similar strategy*, since this proposed classification has no point of comparison with other types of classifications used in the day-to-day clinical practice.

Descriptive Analysis: Descriptive analysis will be performed using absolute frequencies and calculated percentages of the response option for each item. Finally, the absolute frequencies of each response option will be added up and the response percentage will be calculated to find the global acceptability of the anatomical classification of the placenta accreta spectrum, in relation to what was addressed in the survey.

The results are presented in Table 5.

Table of Variables

Variable Name	Definition	Type of variable	Operational Level	Measure Summary	Objective that resolves
1. Identifier number in the study	Unique consecutive number that identifies the participant in the study	Quantitative	Round numbers starting from 1	NA	NA
2. Date of surgery for PAS treatment	dd/mm/yyyy on which surgical management is performed for the treatment of placental accretism	NA	dd/mm/yy	NA	NA
3. Maternal age	Time in years, from the participant's date of birth to the date of visit, due to suspicion or diagnosis of PAS	Quantitative	Numbers greater ≥ 18	Central tendency and dispersion	1
4. Gravity	Number of pregnancies the patient has had at the time of the first visit for suspected or diagnosed PAS. (Considering the current pregnancy)	Quantitative	Number	Central tendency and dispersion	1
5. Parity	Number of previous deliveries of the patient at the first consultation for suspected or diagnosed PAS.	Quantitative	Number	Central tendency and dispersion	1
6. Previous Cesarean-sections	Number of previous cesarean sections the patient has had until the first visit for suspected or confirmed diagnosis of PAS	Quantitative	Number	Central tendency and dispersion	1

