The invited hospitals are institutions that already applying the proposed classification or that were previously trained to implement this classification, in addition to the surgical techniques that might be required in each case. Prior to this study, some health centers were trained by the principal investigator of this study via telemedicine (28). Likewise, the topographic classification of PAS been proposed (*Annex 1*) will be socialized and reinforced to the obstetrician-gynecologists who manage patients with placenta accreta spectrum, aiming to achieve a correct and standardized classification in all the participating centers, which reduces measurement bias. Prospective data collection will start from the moment the medical history is taken from the institutional database of each participating center, considering the qualitative and quantitative variables of the chosen population, that are related to the surgical intervention and the clinical outcomes during the postoperative period. In this case, the immediate postoperative period will be followed up until the time of discharge. All the information obtained will be typed and saved in the RedCaP platform, to have traceability of the information and ensure the confidentiality of the patient's data is maintain all the time.

The participating hospitals will make the necessary arrangements at the local level for the

execution of the study, sign a confidentiality agreement that states they are collaborating on this study with Fundación Valle de Lili. It will be the responsibility of each participating center to comply with local and international regulations on good clinical practices in research and the stipulations stated by the ethics committee.

Once the collection of patient data has been completed, a survey will be carried out to evaluate the acceptability of the topographic classification by the group of obstetrician-gynecologists who manage placenta accreta patients in each participating hospital. Given that for this last objective, the calm environment of those being evaluated could be disrupted by requesting their participation, prior to starting the survey, authorization will be requested for the use of the participants' data, their authorization being understood as affirmative if they choose "I accept" in the statement that provides that information, prior to the beginning of the questionnaire and their refusal if they do not choose to accept and/or do not complete the survey.

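### The acceptability survey can include the study's own investigators, and Table 5 as planned gives no way to see the result without them

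*Combined protocol and SAP*

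**What the plan says.** **Who answers.** Study population lists, as its second group, "Obstetrician-gynecologists working in participating medical centers". Data collection techniques narrows this. The survey, given after patient data collection has ended, "will be administered to the group of obstetricians who manage placenta accreta at the participating centers". The rule for the individual respondent reads: "Each participating physician who has applied the topographic classification to the patients treated during the study period, will complete the survey only once". Neither section makes an exception for people with a role in the study.

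**Where the study team sits.** One of the six participating centers houses the principal investigator's team. On data entry the protocol says: "At Fundación Valle del Lili, the task will be performed by the research assistants' that are part of the principal investigators team".

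**How respondents came to the classification.** Operational Aspects says: "The invited hospitals are institutions that already applying the proposed classification or that were previously trained to implement this classification". It adds that "some health centers were trained by the principal investigator of this study via telemedicine", and that the classification "will be socialized and reinforced to the obstetrician-gynecologists who manage patients with placenta accreta spectrum".

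**How answers are analyzed.** Under Specific Objective 3: "Descriptive analysis will be performed using absolute frequencies and calculated percentages of the response option for each item". The counts for each response option are then added over all items to give a global figure. Table 5 has 11 statements, one column per response option, a TOTAL row and a single N. The Table of Variables contains no respondent characteristics.

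**What the result is for.** Specific Objective 3 is exploratory and confined to the participating centers. The Research Hypotheses section goes further: it states that acceptability is high among specialists who manage the condition, without restricting this to those centers and without a threshold for high.

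**The concern.** An acceptability survey is read as the verdict of users on a tool. A physician who is running or authoring the study of that tool is also a user, but not a disinterested one. If such physicians answer and are pooled with everyone else, the reader cannot tell acceptance by ordinary users from endorsement by the study team.

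This matters more when respondents are few. The survey is confined to physicians at six centers who applied the classification to study patients, and no expected number is given. With no threshold for high acceptability, any upward shift counts in favor of the hypothesis. The survey serves one of the three specific objectives. Patient outcomes and the patient sample size are not affected.

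**Working it through.** **1. Is there a plan figure to reproduce?** No. The documents state no survey sample size, precision or threshold. The only sample-size calculation concerns patients and does not bear on this point.

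**2. Does the rule admit investigators?** Set the two criteria side by side: the respondent must be a specialist at a participating center, and must have applied the classification to study patients. An investigator or author who operates on study patients meets both, and no visible text removes that person.

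**3. Could the planned output separate them?** No. Table 5 is split only by response option. Operational Aspects ties the analysis to the variable table and the blank tables, and neither carries study role.

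**4. How large could the effect be on one item?** All inputs here are assumptions, because the documents give none. Let f be the investigators' share of respondents, P their agreement and q the agreement of the others:

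pooled agreement = f × P + (1 − f) × q

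For a positively worded item with P = 100% and q = 60%:

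| f | Calculation | Pooled | Shift |
|---|---|---|---|
| 10% | 0.1 × 100 + 0.9 × 60 | 64% | 4 points |
| 20% | 0.2 × 100 + 0.8 × 60 | 68% | 8 points |
| 40% | 0.4 × 100 + 0.6 × 60 | 76% | 16 points |

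A smaller gap shrinks the effect. With q = 80%, P = 90% and f = 10%, the pooled figure is 0.1 × 90 + 0.9 × 80 = 81%, a shift of 1 point.

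**5. Does the same effect reach the TOTAL row?** Not at that size. Of the 11 statements, 7 are favorable when agreed with: ease of use, ease of remembering, usefulness, clarity, colleagues' support, patient benefit and better use of resources. Four are unfavorable when agreed with: lawsuits, a missing clinical detail, a difficult work environment and extra resource consumption. A wholly favorable respondent agrees with 7 and disagrees with 4, and so contributes 7/11 = 63.6% agreement to the TOTAL row, not 100%.

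- If the others' agreement across all 11 items is 60%, then f = 20% gives 0.2 × 63.6 + 0.8 × 60 = 60.7%, and f = 40% gives 0.4 × 63.6 + 0.6 × 60 = 61.5%. The shift is about 1 point.
- If 60% instead means that the others answer favorably on each item (60% agree on positive items, 40% on negative ones), their TOTAL agreement is (7 × 60 + 4 × 40)/11 = 52.7%. The pooled figures are then 0.2 × 63.6 + 0.8 × 52.7 = 54.9% and 0.4 × 63.6 + 0.6 × 52.7 = 57.1%, shifts of about 2 and 4 points.

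On either reading the TOTAL row hides most of a difference that single items would show (8 and 16 points at the same shares).

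**The case against.** The strongest reply has five parts.

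- **No text says an investigator will answer.** This stands. A reader might infer that the principal investigator or site leads will be among the respondents. The documents show only that the rule admits them. How many would qualify is unknown.
- **The survey form is not in the supplied text.** This also stands. Annex 2 may already ask for role or center, so the plan cannot be faulted for failing to record it. What can be said is that the visible analysis text and Table 5 make no use of such an item.
- **Training is not a stake in the result.** This stands. A reader might infer that physicians trained by the principal investigator should be counted with the study team. The documents do not support that. Knowledge of the classification is an entry condition for centers, and a user has to know a tool to rate it. Teaching is also reinforced for the very group surveyed, so a trained/untrained split would probably separate few people.
- **A figure such as 68% to 76% does not describe global acceptability.** Correct. Those values apply to one positively worded item under assumed inputs. Step 5 shows why they do not carry over to the TOTAL row.
- **The objective is exploratory and limited to these centers.** True, and surveying users there fits it. The hypothesis, however, is worded more widely, and even an exploratory percentage should let the reader see whose answers it contains.

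None of these replies supplies the missing separation by study role.

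**Conclusion.** The point holds in a limited form, as a low-cost improvement. The respondent rule covers any investigator or author who applied the classification, and the planned analysis cannot show acceptability without them, so the reported result may partly reflect the study team's own view.

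The number of such respondents, and the size and even the existence of a shift, cannot be computed from the documents. Under the stated assumptions (60% agreement among others, 100% among investigators, a share of 10% to 40%), a single positive item would read 64% to 76% instead of 60%. The TOTAL row would move by about 1 to 4 points at shares of 20% to 40%, depending on what the 60% is taken to mean. The documents do not support a claim that the survey result is inflated by a known amount.

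**What to change.** 1. Record whether each respondent is an investigator or author of this study, with one yes/no item, unless the survey form already captures it.
2. In Table 5, report every item twice: for all respondents, and again excluding investigators and authors, with the number of respondents in each set. Make the comparison item by item, not on the TOTAL row.
3. Word the conclusion on Specific Objective 3 for trained users of the classification at the participating centers, and bring the hypothesis into line with that.

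A split by training and a separate investigators-only column are not needed. The first would show little contrast, and the second could make individuals recognizable in small teams. Subtracting one set from the other still recovers the investigators' combined answers, so this comparison should stay pooled over centers.

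The cost is at most one survey item and one added set of figures. The second set has a smaller denominator and is less precise. The survey is given only after patient data collection ends, so patient data, endpoints and sample size are unaffected.

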Total Complications	31.05%	50%	95.65%	100%
---------------------	--------	-----	--------	------

The sample size was calculated using the openepi web tool, available at: https://www.openepi.com/Menu/OE_Menu.htm. To approximate to a round number the sample calculation, it was used the Cohorts option, considering the unexposed group as the classification option with the lowest percentage of total complications (T1), and the exposed group as the classification option with the highest percentage of total complications (T4). With a confidence level of 95%, power of 80%, ratio of unexposed/exposed = 1, percentage of unexposed positives = 31.05% and percentage of exposed positives = 99.99%; the following results are obtained.

Tamaño muestral: transversal, de cohorte, y ensayo clínico

Nivel de significación de dos lados(1-alpha)	95
Potencia (1-beta,% probabilidad de detección)	80
Razón de tamaño de la muestra, Expuesto/No Expuesto	1
Porcentaje de No Expuestos positivos	31
Porcentaje de Expuestos positivos	100
Odds Ratio:	22000
Razón de riesgo/prevalencia	3.2
Diferencia riesgo/prevalencia	69

	Kelsey	Fleiss	Fleiss con CC
Tamaño de la muestra - Expuestos	8	7	9
Tamaño de la muestra- No expuestos	8	7	9
Tamaño total de la muestra	16	14	18

It is expected that as we progress through the 7 option types of the proposed classification, we will have fewer patients; this implies that the classification with the lowest recruitment expectation will be T5b. All logistic efforts and recruitment strategies will be made to obtain at least 9 patients in the least frequent option type, considering the Fleiss sample size on continuous adjustment. Due to the difficulty of obtaining a significant and similar number of patients on each option type, it is considered appropriate to include all cases of PAS who visit the participating centers and meet the admission criteria in the 2-year period, with the possibility of extension, if the minimum number of cases for each option

Data collection techniques

The group of obstetrician-gynecologists will inform the principal investigator or study coordinator about patients that can be included in the study. Once it is confirmed that they meet the inclusion criteria, the data will be collected from the electronic or paper-based medical records of the hospital, protecting the identity of the patients at all times.

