In both cases, the null hypothesis (H_0) indicates that the mean or median numbers of the 7 subpopulations are equal; the alternate hypothesis (H_a) refers to the above being different. If the p-value indicated by those tests is ≥ 0.05 (5%), it can be stated that there are no statistically significant differences between the mean or median numbers of the 7 subpopulations, with 95% confidence, which is set for the study. If the p-value is < 0.05 , the hypothesis of having no difference in the mean or median numbers (H_0) is rejected. That does not imply that a particular subgroup is superior or inferior to another.

For qualitative variables, a statistical test of the difference in proportions of the 7 subgroups (independent groups) will be performed by means of the Chi-square test. A result with a p-value ≥ 0.05 (5%) can be interpreted as: the proportions of the variable in question do not differ, in terms of statistical significance, among the seven groups. In case the p-value is < 0.05 indicates that there are statistically significant differences between at least two of the seven groups with respect to the proportions of the variable addressed. This does not imply that a particular subgroup is superior or inferior to another.

The results are shown in Table 3.

Specific Objective 2: To analyze the clinical outcomes of patients diagnosed with placenta accreta spectrum according to anatomical classification.

Descriptive Analysis: Stratification by subgroups will be performed according to the anatomical classification of PAD as follows: T1, T2a, T2b, T3, T4, T5a and T5b. Qualitative variables will be summarized as percentages and presented as absolute frequencies. For quantitative variables, the normality distribution will be determined by means of the Kolmogorov statistic.

Smirnov (sample size greater than 50 patients is expected), where a result of p-value >0.05 would comply with the assumption of normality. For variables with normal distribution, mean and standard deviation will be determined; and for variables without normal distribution, median and interquartile ranges (Q1 - Q3) will be indicated.

Inferential Analysis: For quantitative variables, a statistical test of the difference in means of the 7 subgroups (independent groups) will be performed by means of one-way ANOVA for independent groups. If the variable does not have a normal distribution, the Kruskal-Wallis test will be performed.

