In both cases, the null hypothesis (H_0) indicates that the means or medians of the 7 subpopulations are equal; the alternate hypothesis (H_a) refers to the above being different. If the p-value indicated by these tests is ≥ 0.05 (5%), it can be stated that there are no statistically significant differences between the means or medians of the 7 subpopulations, with 95% confidence, which is set for the investigation. If the p-value is < 0.05 , the hypothesis of equality of population means or medians (H_0) is rejected. This does not imply that a particular subgroup is superior or inferior to another.

For qualitative variables, a statistical test of the difference in proportions of the 7 subgroups (independent groups) will be performed by means of the Chi-square test. A result with a p-value ≥ 0.05 (5%) can be interpreted as: the proportions of the variable in question do not differ in terms of statistical significance, among the seven groups. In case the p-value is < 0.05 , it indicates that there are statistically significant differences between at least two of the seven groups with respect to the proportions of the variable been assessed. That does not imply that a particular subgroup is superior or inferior to another.

The results are shown in Table 4.

Specific Objective 3: To explore the acceptability of the topographic classification of

placenta accreta spectrum among obstetrician-gynecologists at the participating medical centers.

In the scientific literature there is no validated scale to evaluate the acceptability of a new clinical classification, which in this case is proposed as a topographic classification of PAS. After an exhaustive search, it was concluded that the *The Ottawa Acceptability of Decision Rules Instrument* would be utilized, which is a widely used instrument to evaluate the acceptability of a norm among physicians. There is no linguistic adaptation to Spanish, so a direct translation of its content was made.

After the principal investigator had reviewed it, was necessary make adaptations to some items, which were:

- a) Change the original term "norm" to "*anatomical classification for PAS*". In all items.

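### The normality gate ignores variance, so with very unequal type sizes the planned ANOVA / Kruskal-Wallis rule can reject too often if the rarer types are the more variable ones

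*Combined protocol and SAP*

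**What the plan says.** Under Data Management and Statistical Analysis, Specific Objectives 1 and 2 share one rule. For quantitative variables "the normality distribution will be determined by means of the Kolmogorov Smirnov statistic (sample size greater than 50 patients is foreseen"), and a p-value above 0.05 counts as normal. A normal variable is compared across the seven types "by means of one-way ANOVA for independent groups"; otherwise Kruskal-Wallis is used. For either test, Objective 2 states that "the null hypothesis (H_0) indicates that the means or medians of the 7 subpopulations are equal", and H0 is rejected at p < 0.05. Objective 1 has the same reading.

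Neither objective mentions equal variances, a test that allows unequal variances, or the equal-shape condition that the median reading needs. The text does not say whether the Kolmogorov-Smirnov (KS) test is run on the pooled variable or within type, or whether it is corrected for an estimated mean and SD.

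On group sizes, the sample size section cites a series of 248, 44, 23 and 11 women in four types. It adds: "It is expected that as we progress through the 7 option types of the proposed classification, we will have fewer patients". The recruitment target is to "obtain at least 9 patients in the least frequent option type".

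**The concern.** One-way ANOVA pools the within-group variances, weighted by group size. If one large type has small spread and several small types have large spread, the pooled variance sits close to that of the large type and understates the noise in the small types' means. The F statistic is then too large even when all means are equal. A normality test cannot warn of this, because it does not compare variances between types.

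The other branch has a related fault. Kruskal-Wallis tests whether the distributions are the same. When spreads differ, it can reject more often than 5% although all medians are equal, so its p-value does not support the stated conclusion.

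The study sets out to relate the classification to clinical outcomes. No regression model is planned, so these p-values are its only inferential evidence on quantitative variables.

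**Working it through.** **Inputs from the documents.** Seven types; test level 0.05; cited series 248/44/23/11, so type 1 is 248/326 = 76%; target minimum of nine in the rarest type; numbers expected to fall from type to type. No SD by type is given, and no total N beyond more than 50.

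**The plan's own figure.** The minimum of nine comes from "With a confidence level of 95%, power of 80%, ratio of unexposed/exposed = 1" and "percentage of unexposed positives = 31.05% and percentage of exposed positives = 99.99"%, two-sided. With mean proportion 0.6552 and difference 0.6894:
- Fleiss: [1.960·√(2·0.6552·0.3448) + 0.8416·√(0.9999·0.0001 + 0.3105·0.6895)]² / 0.6894² = 6.13, so 7.
- Kelsey: (1.960 + 0.8416)²·2·0.6552·0.3448 / 0.6894² = 7.46, so 8.
- Fleiss with continuity correction: (6.13/4)·[1 + √(1 + 4/(6.13·0.6894))]² = 8.79, so 9.

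All three match. The plan states no error rate for the ANOVA / Kruskal-Wallis step.

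**Why size and spread interact.** With equal means, k groups, total N and group variances σᵢ²:
- expected between-group mean square = Σ(1 − nᵢ/N)σᵢ² / (k − 1)
- expected within-group mean square = Σ(nᵢ − 1)σᵢ² / (N − k)

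Take 60 in type 1, nine in each of the other six (N = 114), SD 1 in type 1 and 2 elsewhere:
- between: [(1 − 60/114)·1 + 6·(1 − 9/114)·4]/6 = 3.76
- within: (59·1 + 48·4)/107 = 2.35
- ratio: 1.60, where a valid F test has 1

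With SD 0.5 elsewhere the ratio is 0.31/0.66 = 0.47, so the test becomes conservative. With 20 in every type the ratio is exactly 1.

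**Simulation, normal data with equal means** (4000 runs per scenario). The gate is pooled KS with estimated mean and SD. Entries are rejection rates.

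| Sizes | SD, other types ÷ type 1 | Mean-square ratio | ANOVA | Kruskal-Wallis | Gated rule | Welch |
|---|---|---|---|---|---|---|
| 60 + 6×9 | 0.5 | 0.47 | 0.2% | 0.6% | 0.2% | 5.4% |
| 60 + 6×9 | 1 | 1.00 | 5.5% | 4.7% | 5.5% | 6.7% |
| 60 + 6×9 | 1.5 | 1.38 | 16.3% | 10.2% | 16.3% | 6.4% |
| 60 + 6×9 | 2 | 1.60 | 23.9% | 13.7% | 23.9% | 5.8% |
| 100 + 6×9 | 1.5 | 1.55 | 20.8% | 11.3% | 20.8% | 5.4% |
| 100 + 6×9 | 2 | 1.93 | 35.9% | 18.6% | 35.7% | 6.1% |
| 7×20 | 2 | 1.00 | 5.5% | 4.9% | 5.5% | 5.2% |

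Other sizes, all assumed:
- 248/22/22/23/11/9/9 (the cited type 2 split equally, nine added for each type 5 group), ratio 2: gated rule 42.9%.
- T1 = 30, 60 or 150 with nine in each other type, ratios 1.5 to 2: 10-14%, 16-24% and 26-44%.
- A gentler gradient, 60/30/25/20/15/12/9, ratios 1.5 to 2: 8-14%.

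**Does the gate help?** At unequal sizes, normal data with twofold spread passed as normal in 96-99.6% of runs, so ANOVA was almost always used.

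**Skewed data with equal medians** (lognormal, log-SD 0.5 in type 1, 1.5 to 2 times larger elsewhere): the gated rule rejected in 10.8-13.4% at 60 + 6×9 and 11.3-18.0% at 100 + 6×9. Kruskal-Wallis alone gave 9.5-13.5% and 11.1-17.9%, so at these sizes the excess comes mostly through that branch. Over all sizes tried the range is about 8-23%.

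**Does Welch repair it?** With normal data and unequal sizes, Welch rejected 5-7% throughout. On identical lognormal groups, raw-scale Welch rejected 7-11% in one set of runs and 9-14% in another, while log-scale Welch rejected 4-7%. On identical Poisson counts (mean 1.5) Welch rejected 6-9%, against 4-5% for Kruskal-Wallis. The remedy must therefore name the scale.

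**The case against.** **Direction.** A reader might infer that any difference in spread between types inflates the error rate. It does not. The rarer types must be the more variable ones. In the opposite direction the rule is conservative, and with balanced sizes the gated rate stays at about 5-7%. The documents give no SD by type, so direction and ratio are both assumptions. The Topographic classification section lends the direction some support: it links type 1 to less bleeding, and the rare low-parametrial and trigone types to more. Spread often rises with the mean for a positive, skewed measure. That is plausible, not documented.

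**Sizes.** Nine is the target for the least frequent type only, so nine in all six smaller types is near the worst case. The graded sizes give 8-14%. Sizes built on the cited series, however, still give 43% at ratio 2.

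**The gate itself.** A reader might infer that KS passes nearly everything as normal. It does not. Lognormal data with log-SD 0.5 and equal spread passed in 50% of runs at N = 114 and 29% at N = 154, and in 2.9% and 0.6% with the Lilliefors cut-off. A pooled, uncorrected test is also an inference. The remark about more than 50 patients favours pooling, but the sentence follows the stratification by type. The gate does not cause the inflation; it fails to detect the cause.

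**Scope.** Blood loss in ml is the only quantitative variable assigned to Objective 2. Surgical time and postoperative stay are assigned to Objective 1 and appear in neither Table 3 nor Table 4. Table 4 reports hemorrhage by stage, with no row in ml. This narrows the point without removing it, because the text applies the rule to all quantitative variables.

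**Interpretation.** The plan cautions that rejection does not show one subgroup to be superior or inferior. That guards against ranking types, not against a false claim that means or medians differ. The documents also expect real differences in bleeding, but a test must still hold its level where none exist.

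**Conclusion.** The concern holds conditionally. The gate, ANOVA without a variance condition and the median reading of Kruskal-Wallis are all in the text, and strong imbalance is the plan's own expectation.

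If the rarer types are 1.5 to 2 times more variable, the false-positive rate is about 8-25% at moderate imbalance and up to about 45% at extreme imbalance with near-normal data. It is about 8-23% with skewed data of equal medians. If spreads are equal it is about 5%. If the rarer types have half the spread it is about 0-3%, and real differences may be missed. The cause is unequal variance combined with unequal sizes.

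These rates rest on assumed SD ratios, assumed sizes for seven types and a pooled, uncorrected KS test. The misstated null for Kruskal-Wallis needs correcting whatever those values are. The variables most affected are blood loss, surgical time and stay.

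**What to change.** Amend Specific Objectives 1 and 2 before any analysis by type:

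- Remove the KS test as the selector of the comparison.
- Pre-specify Welch's ANOVA on the log scale for blood loss, surgical time and postoperative stay, and on the raw scale for roughly symmetric variables (maternal age, gestational age at delivery). State how a stay of zero days is handled on the log scale.
- Use Kruskal-Wallis for counts (gravidity, parity, previous cesareans) and as a sensitivity analysis elsewhere.
- Restate the Kruskal-Wallis null in both objectives as equal distributions, not equal medians.
- If a fallback for very small types is kept, fix its minimum size in advance.
- Say where blood loss in ml, surgical time and stay will be reported, since the blank tables have no rows for them.

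The cost is analysis-plan wording only; no data collection changes. Log-scale results are ratios of geometric means, which need a sentence of explanation, and Welch loses a little power if variances are in fact equal.
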